12. History of a MI, unstable angina leading to hospitalization, coronary artery bypass graft surgery, percutaneous coronary intervention, uncontrolled cardiac arrhythmia, carotid surgery or stenting, stroke, transient ischemic attack, valve replacement surgery, carotid revascularization, endovascular procedure or surgical intervention for peripheral vascular disease within 3 months prior to the screening visit
13. History of New York Heart Association (NYHA) Class IV heart failure within 12 months before screening.
14. Age <18 years at the screening visit
15. History of cancer within the past 5 years, except for adequately treated basal cell skin cancer, squamous cell skin cancer, or in situ cervical cancer
16. Use of any active investigational drugs (except alirocumab) within 1 month or 5 half-lives prior to the screening visit, whichever is longer
17. Conditions/situations such as:
 - a. Any clinically significant abnormality identified at the time of screening that, in the judgment of the investigator or any sub-investigator, would preclude safe completion of the study or constrain endpoints assessment; eg, major systemic diseases, patients with short life expectancy

- b. Considered by the investigator or any sub-investigator as inappropriate for this study for any reason, eg:
- Deemed unable to meet specific protocol requirements, such as scheduled visits
 - Investigator or any sub-investigator, pharmacist, study coordinator, other study staff or relative thereof directly involved in the conduct of the protocol, etc
 - Presence of any other conditions (eg, geographic or social), either actual or anticipated, which the investigator feels would restrict or limit the patient's participation for the duration of the study
18. Laboratory findings during the screening period (not including randomization labs):
- Positive test for hepatitis B surface antigen and/or hepatitis C antibody (associated with a positive HCV RNA polymerase chain reaction)
 - Positive serum beta-human chorionic gonadotropin or urine pregnancy test in women of childbearing potential (WOCBP)
 - eGFR <30 mL/min/1.73 m² (calculated by central lab)
 - Alanine aminotransferase (ALT) or aspartate aminotransferase (AST) >3 x upper limit of normal (ULN) (1 repeat lab is allowed)
 - CPK >3 x ULN (1 repeat lab is allowed)
 - TSH >1.5 x ULN of the central laboratory (1 repeat lab is allowed) for patients not on thyroid replacement therapy
19. Known hypersensitivity to mAb therapeutics

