9.4.3. Other Events that Require Accelerated Reporting to Sponsor

The following events also require reporting to the sponsor (or designee) within 24 hours of learning of the event:

Symptomatic Overdose of Study Drug: Accidental or intentional overdose of at least 2 times the intended dose of study drug within the intended therapeutic window, if associated with an AE.

Pregnancy: Although pregnancy is not considered an AE, it is the responsibility of the investigator to report to the sponsor (or designee), within 24 hours of identification, any pregnancy occurring in a female or female partner of a male, during the study or within 24 weeks of the last dose of study drug. Any complication of pregnancy affecting a female study patient or female partner of a male study patient, and/or fetus and/or newborn that meets the SAE criteria must be reported as an SAE. Outcome for all pregnancies should be reported to the sponsor.

Adverse Events of Special Interest: All AESIs, serious and nonserious, must be reported within 24 hours of identification using the same reporting process as for SAE reporting, per Section 9.4.2.

Adverse events of special interest (serious or non-serious) for evinacumab include the following:

- Anaphylactic reactions
- Allergic reactions and/or local injection site reactions that require consultation with another physician for further evaluation or requiring medical treatment
- Increase in ALT or AST: ≥ 3 x ULN (if baseline <ULN), or ≥ 2 times the baseline value (if baseline \geq ULN)
- Pregnancy
- Symptomatic overdose with investigational medicinal product
- Neurocognitive events
- New onset of diabetes (see definition below)
- Pancreatitis

Adverse events of special interest for alirocumab include the following:

- Increase in ALT: ALT ≥ 3 x ULN (if baseline ALT <ULN), or ALT ≥ 2 times the baseline value (if baseline ALT \geq ULN)
- Allergic events and/or local injection site reactions that require consultation with another physician for further evaluation

- Pregnancy
- Symptomatic overdose with investigational medicinal product
- Neurologic events that require additional examinations/procedures and/or referral to a specialist
- Neurocognitive events
- Cataracts
- New onset of diabetes: The definition of new onset of diabetes (NOD) will be the following:
 - Type 1 or type 2 diabetes TEAE (grouping of Medical Dictionary for Regulatory Activities [MedDRA®] terms will be specified in the SAP)and/or

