5.8.3. Clinical Laboratory Measurements

For respective treatment period (DBTP and OLTP), clinical laboratory parameter actual values (quantitative) and change from baseline values will be descriptively summarized at baseline and each post-baseline visit (collected up to the day of last dose of study treatment +28 days) by at least patient number, mean, median, Q1, Q3, SD, minimum and maximum. Clinical laboratory parameters mean changes from baseline, with the corresponding SE, can be plotted at each visit in the case results warrant further investigation. These parameters will be presented by the biological functions defined in Section 4.8.2. For glucose, only fasting samples will be included in the summaries.

Individual patient laboratory parameter measurements will be additionally evaluated by PCSV criteria (See Appendix 10.4), specifically identifying patients with at least one post-baseline measurement that meets the PCSV criteria within the respective TEAE periods. These laboratory parameters will be presented by the biological functions defined in Section 4.8.2. The incidence of PCSVs at any time during the respective TEAE periods will be summarized regardless of the baseline level, and again according to the following baseline categories:

- Normal (according to PCSV criterion/criteria)/missing
- Abnormal according to PCSV criterion or criteria

Patient listings of laboratory measurements that meet PCSV criteria will be provided for the report appendix. For those laboratory parameters that don't have an associated PCSV criteria, similar summary tables can be provided based on measurements outside the central laboratory normal ranges, if applicable.

Drug-induced liver injury

For respective treatment period (DBTP and OLTP), an evaluation of drug-induced serious hepatotoxicity (eDISH) with the graph of distribution of peak values of ALT versus peak values of total bilirubin will also be presented using post-baseline values during respective TEAE periods. Note that the ALT and total bilirubin values are presented on a logarithmic scale. The graph will be divided into 4 quadrants with a vertical line corresponding to 3 x ULN for ALT and a horizontal line corresponding to 2 x ULN for total bilirubin.

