Patient listing of possible Hy's law cases identified by treatment group (i.e., patients with any elevated ALT > 3 x ULN, and associated with an increase in bilirubin > 2 x ULN, concomitantly or not) with ALT, AST, ALP, total bilirubin, and if available direct and indirect bilirubin will be provided.

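### The SAP's three joint aminotransferase-bilirubin outputs select on ALT alone, although the protocol's evinacumab liver event of special interest is ALT or AST, so an AST-led case must be linked by hand

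*SAP*

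**What the plan says.** **Protocol.** Section 9.4.3 lists "Increase in ALT or AST" among the AESIs for evinacumab. The limit is 3 x ULN or more when baseline is below ULN, and otherwise at least twice baseline. AESIs "must be reported within 24 hours of identification using the same reporting process as for SAE reporting". The parallel entry for alirocumab in the same section names ALT only. Exclusion at entry (section 6.2.2, laboratory findings) treats the two enzymes alike, at more than 3 x ULN. Both versions of the protocol, adult and 12 years or older, read the same way on these points.

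**SAP.** Three outputs join an aminotransferase with bilirubin:

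- The eDISH figure (5.8.3) is a "graph of distribution of peak values of ALT versus peak values of total bilirubin", with a "vertical line corresponding to 3 x ULN for ALT and a horizontal line corresponding to 2 x ULN for total bilirubin".
- The listing of possible Hy's law cases (5.8.3) takes "patients with any elevated ALT > 3 x ULN, and associated with an increase in bilirubin > 2 x ULN, concomitantly or not". AST is a printed column, but only for patients already selected on ALT.
- The combined row in the potentially clinically significant value (PCSV) table of Appendix 10.4 requires ALT above 3 x ULN and total bilirubin above 2 x ULN.

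AST otherwise appears singly. Appendix 10.4 gives it the same five cut-offs as ALT (2, 3, 5, 10 and 20 x ULN), and 5.8.3 summarises it descriptively. The hepatic AESI in Appendix 10.3 rests on the drug-related hepatic disorder SMQ plus these same PCSV, Hy's law and eDISH items. It adds no rule for AST with bilirubin.

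**The concern.** The joint enzyme-bilirubin outputs exist to pick out patients in whom both abnormalities occur. The protocol counts AST equally with ALT when it defines a liver event for the study drug and when it screens patients, and the SAP gives AST the same single-parameter cut-offs. AST drops out only at the joint step, and the SAP gives no reason. The listing is otherwise a sensitive screen, since it does not require the two rises to coincide in time.

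The stake is how easily one kind of case can be seen. The trial plans about 57 patients, 38 of them on evinacumab, so individual liver cases carry weight when the safety data are read. Protocol section 10.4.9.1 says the first-step analysis may go into a submission. Lomitapide and mipomersen are permitted background drugs, and the protocol's introduction associates both with hepatic abnormalities.

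**Working it through.** No power, alpha or sample-size figure bears on this, so the check applies each rule to one patient. The values are assumed for illustration: normal baseline, then peak AST 4 x ULN, ALT 2.5 x ULN and total bilirubin 2.5 x ULN.

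| Output | Rule | Result for this patient |
|---|---|---|
| Evinacumab AESI, protocol 9.4.3 | ALT or AST at least 3 x ULN (baseline below ULN) | Met through AST: 4 ≥ 3 |
| Possible Hy's law listing, SAP 5.8.3 | ALT > 3 and bilirubin > 2 | Not selected: 2.5 is not > 3 |
| Combined PCSV row, Appendix 10.4 | ALT > 3 and bilirubin > 2, with baseline condition | Not met: 2.5 is not > 3 |
| eDISH plot, SAP 5.8.3 | ALT line at 3, bilirubin line at 2 | Plotted at (2.5, 2.5): bilirubin-only quadrant, AST not shown |
| Single AST PCSV, Appendix 10.4 | AST > 3, baseline ≤ 3 | Met: 4 > 3 |
| Single bilirubin PCSV, Appendix 10.4 | Bilirubin > 2, baseline ≤ 2 | Met: 2.5 > 2 |

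The exact values do not matter. Any patient with AST > 3, ALT ≤ 3 and bilirubin > 2 (all x ULN) fails the enzyme condition of the listing and of the combined row, and lies at or to the left of the ALT line on eDISH. The two abnormalities are recorded in separate PCSV rows. Their link can be recovered only by matching patient identifiers across the AST and bilirubin listings.

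With ALT or AST as the condition, the qualifying enzyme value is max(2.5, 4) = 4, and 4 > 3. The patient then enters the listing and the combined row, and moves to (4, 2.5) on eDISH, in the quadrant with both raised.

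**The case against.** The strongest reply is that the case would still be visible. SAP 5.8.3 commits to patient listings of laboratory measurements that meet PCSV criteria, and protocol section 10.4.4.2 calls for listings that flag them. The patient above would be flagged for both AST and bilirubin, and matching the two in a trial of about 57 is not hard. The same patient meets the evinacumab AESI and so falls under 24-hour reporting, would come under the hepatic SMQ if an adverse event were coded, and appears on eDISH above the bilirubin line. All of this stands. A reader might infer that such a case goes undetected, and the documents do not support that.

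A second reply is that the SAP contradicts nothing. The protocol specifies neither an eDISH plot nor a Hy's law listing, and it leaves the PCSV criteria to the SAP. A rule for expedited reporting of one enzyme does not fix the axis of a descriptive figure. This also stands. A reader might infer a breach of a protocol-specified analysis, but there is none. Nor is AST named in protocol section 7.4.2.1 among the reasons for stopping study drug: it is a reporting trigger only.

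Third, the supporting context is limited. The protocol's remarks on lomitapide and mipomersen are not specific to AST, so they do not show that AST would rise without ALT. Nothing in the documents says that a single liver case would decide the outcome, and that inference should not be drawn.

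What remains is that no output labels the patient as a joint case, while the equivalent patient with the enzyme values reversed is labelled in all three.

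**Conclusion.** The point holds as a gap in descriptive joint case-finding. All three joint outputs select on ALT, the protocol's liver event for the study drug is ALT or AST, and a patient with AST > 3, ALT ≤ 3 and bilirubin > 2 x ULN is identified as a joint case by none of them.

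Its practical size is unknown, because the documents give no basis for estimating how often the pattern would occur. The primary endpoint, type I error, power and efficacy conclusions are untouched, and safety summaries carry no formal testing (SAP 5.8). The conclusion rests on the written definitions alone. The worked patient shows how the rules behave and is not evidence that such patients exist. The change is worth making as a cheap improvement.

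**What to change.** In SAP 5.8.3, select possible Hy's law cases on ALT or AST above 3 x ULN with total bilirubin above 2 x ULN, and keep the existing allowance that the rises need not coincide. Make the same change in the combined row of Appendix 10.4, with the baseline condition restated so that it refers to the enzyme that qualifies. In the eDISH figure, plot the peak of the higher of ALT and AST in multiples of ULN, or keep the ALT plot and add an AST panel. Print CPK in the listing.

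The cost is SAP wording and a programming condition. No new data are needed, since AST and CPK are already collected, and the schedule of events places CPK at the same visits as blood chemistry. The downside is that some AST rises of muscle origin may be listed; CPK from the same visits helps to identify them. The SAP's overview allows revision on blinded data before the first-step database lock. If that point has passed, the same outputs can be added as supplementary displays and labelled as such.

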5.8.4. Analysis of Vital Signs

For respective treatment period (DBTP and OLTP), the vital sign actual values and change from baseline values obtained while sitting will be descriptively summarized at baseline and each post-baseline visit (collected up to the day of last dose of study treatment +28 days) by at least patient number, mean, median, Q1, Q3, SD, minimum and maximum. Vital sign mean changes from baseline, with the corresponding SE, can be plotted at each visit in the case results warrant further investigation.

Individual patient vital sign measurements (regardless of sitting position) will be additionally evaluated by PCSV criteria, specifically identifying patients with at least one post-baseline measurement that meets the PCSV criteria within the TEAE period. The incidence of PCSVs at any time during the respective TEAE periods will be summarized regardless of the baseline level, and again according to the following baseline categories:

- Normal (according to PCSV criterion/criteria)/missing
- Abnormal according to PCSV criterion or criteria

Patient listings of vital sign measurements that meet PCSV criteria will be provided for the report appendix.

5.8.5. Analysis of 12-Lead ECG

For respective treatment period (DBTP and OLTP), ECG parameters will be described through an overall interpretation of ECG status (e.g. normal, abnormal [clinically significant (Yes/No)]). The count and percentage of patients with at least 1 abnormal post-baseline ECG during the respective TEAE period will be summarized according to the following baseline status categories:

- Normal/missing;
- Abnormal

5.8.6. Physical Exams

A list of patients with any clinically significant abnormality results will be generated.

5.9. Analysis of Other Variables

The summary of results for other variables will be presented separately for the DBTP and OLTP, unless otherwise noted. Summaries for the DBTP will be presented by treatment groups (evinacumab, placebo) containing patients from the double-blind safety analysis set. Summaries for the OLTP will be presented by all patients and by treatment group in DBTP (i.e., evinacumab, placebo), for patients in the open-label safety analysis set. No formal inferential testing will be performed for either period. Summaries will be descriptive in nature.

All measurements, scheduled or unscheduled, fasting or not fasting, will be assigned to Global Analysis Windows (Appendix 10.2) in order to provide an assessment for all post-baseline visit.

Hs-CRP, HbA1c, HDL-C, Apo A1, and Apo B/Apo A1 ratio parameters will be summarized for the number of patients with data, mean, SD, median, minimum, maximum, Q1 and Q3 by analysis visit during the treatment period. The medians (with Q1-Q3) will be plotted for hs-CRP, and means (+/- SE) for HbA1c, HDL-C, Apo A1, and Apo B/Apo A1 ratio. Applying the PCSV criteria at any time during the TEAE period, the number of patients (and percentages) meeting the criteria will be summarized.

Correlations between HoFH genotype status and lipid parameters will be explored (e.g., plot of mean percent change from baseline \pm SE in lipids over time by genotype).

5.10. Analysis of Pharmacokinetic Variables

Descriptive statistics of concentrations of total evinacumab, total ANGPTL3, total alirocumab and total PCSK9 will be presented. Mean concentrations of each analyte will be tabulated by visit and treatment group, with concentrations below the LLOQ set to zero.

Plots of the mean concentrations (linear and log scales) will be presented by nominal sampling time. Plots of the individual concentrations (linear and log scales) will be presented by actual sampling time. In the linear-scaled plots, concentrations below the LLOQ will be set to zero; in the log-scaled plots, concentrations below the LLOQ will be imputed as LLOQ/2.

Descriptive statistics will be provided for concentrations of statins at each sampling time. The ratio of concentration at week 24 over baseline will be presented for individual patient, when available.

Descriptive comparison of concentrations of evinacumab and total ANGPTL3 between Caucasian patients and Japanese patients may be performed, if sufficient data are collected.

When appropriate, relationship between concentrations of evinacumab and LDL-C or other biomarkers may be evaluated descriptively.

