It is also expected that treatment with evinacumab will be well tolerated and have an acceptable safety profile. The accumulated safety information from the completed and ongoing clinical studies is marked by the absence of any important identified risks. There are potential risks that include systemic hypersensitivity reactions, immunogenicity, and embryofetal toxicity. These risks will be managed through careful patient selection and monitoring. For the potential embryofetal toxicity risk, there is a strict risk mitigation plan, including requirements for consistent use of contraception for sexually active male study participants and sexually active female study participants of child-bearing potential.

Patients entering this study should be on a background statin, ezetimibe, and a PCSK9 inhibitor, unless they have a documented history of tolerability issues, lack of efficacy, or other reason. Patients should be on these lipid lowering drugs because of the above mentioned proven CV risk reduction demonstrated in recent CV outcomes trials (ODYSSEY OUTCOMES, FOURIER, IMPROVE-IT). There are 2 PCSK9 inhibitors on the market; evolocumab is approved for use in patients with HoFH in most countries, and alirocumab is currently being evaluated in a double-blind placebo-controlled study in patients with HoFH (study R727-CL-1628, ODYSSEY HoFH). Patients entering this study may be taking either evolocumab or alirocumab. Patients who complete study R727-CL-1628 (ODYSSEY HoFH) with alirocumab are permitted to participate in this study and will continue to receive alirocumab as part of their background LMT. The concurrent use of evinacumab with alirocumab is considered to have an acceptable benefit/risk profile because it could be beneficial and is not considered to pose any safety concerns.

Evinacumab and alirocumab have different mechanisms of action and concomitant administration of both agents is not expected to perturb the action of the other. Rather, their distinct mechanisms of action are anticipated to complement each other to lower LDL-C since they work at different sites of action.

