The safety profile of each agent is considered acceptable and the concurrent use of the 2 agents together is not expected to augment or exacerbate potential adverse events (AEs). Concomitant use of evinacumab and evolocumab was found to have an acceptable safety profile in 4 patients in the R1500-CL-1331 study, a study evaluating evinacumab in 9 patients with HoFH (details of the study are provided in the evinacumab Investigator's Brochure and the Introduction [[Section 1](#)]). No safety signals or adverse effects related to the concomitant use of both agents have been observed. The safety of the use of evinacumab along with alirocumab will be carefully monitored in this study. Safety monitoring will include ongoing reviews by an unblinded Independent Data Monitoring Committee (IDMC), by the sponsor's blinded safety monitoring team (SMT), and by the blinded clinical study team. If significant safety trends or findings are identified by either the

IDMC or the sponsor's blinded study team or SMT, they will be escalated and appropriately evaluated to understand the best course of action.

From the perspective of PK drug-drug interactions, co-administration of evinacumab, alirocumab, and the other possible background LMT (statin, ezetimibe, etc) is not expected to result in drug-drug interactions with each other or other drugs. Evinacumab and alirocumab are both eliminated via a combination of non-saturable, linear, proteolytic degradation and saturable, non-linear target-mediated clearance. The 2 molecules bind to different targets and the target-mediated pathways are entirely independent. Neither evinacumab nor alirocumab are a cytokine or cytokine modulator; therefore, it is not anticipated to interact directly or indirectly with cytochrome P450 enzymes, other drug metabolizing enzymes or drug transporters, which are known to influence the disposition of statins. Conversely, the PK of evinacumab is not expected to be impacted by statins, due to its elimination pathways.

Indeed, the concomitant administration of 2 fully human monoclonal antibodies may be a new treatment paradigm in CV medicine, but not uncommon in other therapeutic areas such as autoimmune disease or oncology. Experience in those areas has demonstrated the use of multiple biologic agents to be acceptable from a safety and tolerability perspective.

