8.2.5. Pharmacokinetic and Anti-Drug Antibody Procedures

8.2.5.1. Drug Concentration Measurements and Samples

Samples for assessment of evinacumab and alirocumab concentration will be collected at time points listed in [Table 3](#) and [Table 4](#). They will be collected predose and at the end of the IV infusion on days when study drug is administered.

[REDACTED]

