10.4.5. Analysis of Drug Concentration and Target Concentration Data

Descriptive statistics of evinacumab concentrations and total ANGPTL3 concentration and alirocumab and PCSK9 concentration at each sampling time will be provided by treatment group. Plots of mean concentrations (linear and log scales) versus time will be presented.

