3.4. Pharmacokinetic (PK) Analysis Set

The PK analysis set is defined as all randomized patients who received any study drug and have at least 1 non-missing post-baseline measurement of evinacumab concentration. Treatment assignments for the DBTP are based on the treatment received (placebo or evinacumab).

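### Mean alirocumab concentrations are to be tabulated by arm with values below LLOQ set to zero and no limit to alirocumab users, so the tabulated mean is the users' mean diluted by the share of users.

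*SAP*

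**What the plan says.** SAP 5.10 names four analytes: "Descriptive statistics of concentrations of total evinacumab, total ANGPTL3, total alirocumab and total PCSK9 will be presented". One rule then covers all of them: "Mean concentrations of each analyte will be tabulated by visit and treatment group, with concentrations below the LLOQ set to zero". Mean plots follow, with values below LLOQ drawn at zero on the linear scale and at LLOQ/2 on the log scale.

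No alirocumab subset is named. The only PK set, in SAP 3.4, consists of "all randomized patients who received any study drug and have at least 1 non-missing post-baseline measurement of evinacumab concentration"; alirocumab use is not a condition. Protocol 10.4.5 is equally unrestricted: "alirocumab and PCSK9 concentration at each sampling time will be provided by treatment group".

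Sampling is also general. Protocol 8.2.5.1 reads "Samples for assessment of evinacumab and alirocumab concentration will be collected at time points" set by the schedule. Table 3 has one combined row for evinacumab, alirocumab, ANGPTL3 and PCSK9, and its footnotes do not confine the alirocumab assay to users.

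Not everyone takes alirocumab. Protocol 3.2.3 says: "Patients entering this study may be taking either evolocumab or alirocumab". The same section also accepts patients on no PCSK9 antibody. The trial supplies alirocumab to patients coming from R727-CL-1628 (Protocol 7.3). Randomization is stratified by apheresis and region only (SAP 2.1).

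**The concern.** Setting values below LLOQ to zero is a reasonable convention for a drug that the patient was given. For a background drug that only some patients take, the zero in a non-user is not a low exposure but the absence of dosing. Averaging it with the users' values gives a number that describes neither group.

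Two consequences follow. The level of the mean is too low by a factor equal to the user share. And two arms with the same exposure among users can show different means merely because chance placed different proportions of users in them. A reader of the table sees one mean per visit and arm and cannot separate user share from exposure.

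**Working it through.** **Inputs from the documents.** Arm sizes are 38 and 19 (SAP 2.2). As a check on these, a two-sample t-test with difference 38, SD 35, 2:1 allocation and two-sided 0.05 has 89.9% power with 42 evaluable patients and 91.9% with 45. Allowing 5% + 15% = 20% loss, 45/0.80 = 56.25, which at 2:1 rounds up to 57 (38 + 19). The planned figure reproduces. The documents give no figure for alirocumab concentrations or for the number of users.

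**Assumptions.** The user share is not stated, so a range is shown. Non-users' samples are assayed for alirocumab and fall below LLOQ. Exposure among users is equal in the two arms.

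**Level of the mean.** Let p be the user share in an arm and m the users' mean.

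Tabulated mean = p × m + (1 − p) × 0 = p × m.

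With m = 100 units:

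| User share | Tabulated mean |
|---|---|
| 10% | 10 |
| 20% | 20 |
| 30% | 30 |
| 50% | 50 |

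**Ratio of arm means.** With equal m, the ratio is p(evinacumab) / p(placebo). Example: 8/38 = 21.1% and 6/19 = 31.6% give tabulated means of 21.1 and 31.6, a ratio of 0.67.

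**How often chance alone does this.** Take K users among 57, with the number in the 38-patient arm hypergeometric and stratification ignored. The probability that the arm means differ by a factor of 1.5 or more is:

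| Users of 57 | Share | Probability |
|---|---|---|
| 9 | 16% | 70% |
| 12 | 21% | 52% |
| 15 | 26% | 34% |
| 20 | 35% | 39% |
| 28 | 49% | 26% |

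The pattern is not smooth because the counts are small whole numbers. With 6 users (11%) there is a 7.6% chance that the placebo arm has none.

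**Change over time within an arm.** If the same patients stay on alirocumab, the mean at a later visit over the mean at baseline is (p × m_later)/(p × m_baseline) = m_later/m_baseline. The user share cancels from the relative change, apart from dropouts. It does not cancel from the absolute level or the absolute change.

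**After restriction to users.** The tabulated mean is m whatever the user share, so the dilution is gone. The ratio between arms is then centred near 1 but still noisy. Assuming a lognormal coefficient of variation of 60% among users, the ratio falls outside 0.80 to 1.25 with probability about 56%, 48% and 35% at 20%, 30% and 50% users. Under the planned rule, user imbalance alone, with no variability in exposure, gives 66%, 59% and 42%. The band and the 60% are illustrative and not from the documents.

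**The case against.** A reader might infer that this table is the trial's check on whether evinacumab alters alirocumab exposure, and that the zero rule could therefore fabricate or hide an interaction. The documents do not support that. Protocol 4.3 names evinacumab concentration as the PK variable, and the PK objective concerns evinacumab. Protocol 3.2.3 says "co-administration of evinacumab, alirocumab, and the other possible background LMT (statin, ezetimibe, etc) is not expected to result in drug-drug interactions", but argues this from elimination pathways and does not say that the trial will test it. No hypothesis, test or between-arm ratio for alirocumab appears anywhere.

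Three further points have weight. Background therapy is to stay stable to week 48 and the combined sample is taken from Day 1, so the within-arm relative change survives the dilution. SAP 5.10 also plans individual plots, where users and non-users are visibly separate. And SAP 5.10 does not name its analysis set: if the laboratory assays alirocumab only in users, non-users are missing and not zero. SAP 4.10 lists three statins without user subsets either, so a programmer might sensibly summarise each drug in its users. Text after Protocol 8.2.5.1 is redacted and cannot be held against the plan.

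What remains is that the visible rule, followed literally, gives the diluted mean, and no visible sentence tells the programmer otherwise.

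**Conclusion.** The point holds as a flaw in a descriptive summary. As written, SAP 5.10 yields an alirocumab mean equal to the user share times the users' mean, and arm means that shift with chance imbalance in users. The size depends on the unstated user share: 20 to 50% users would mean tabulating 20 to 50% of the users' mean. It also rests on non-users' samples being assayed and on SAP 3.4 being the set in use.

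The consequence is limited to this table and the mean plots. The primary result, the safety conclusions and type I error are untouched. A reader might also infer that the by-arm mean of total PCSK9 is broken in the same way. It does mix patients with and without PCSK9 antibodies, but the zero rule does not cause that, and splitting it is a matter of preference.

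**What to change.** In SAP 5.10, state that mean alirocumab concentrations are summarised and plotted only in patients with recorded alirocumab use, with n and the number below LLOQ shown for each visit and arm. Apply the zero rule (LLOQ/2 on the log scale) to alirocumab only in those patients. If the laboratory already assays users alone, say so in the same sentence.

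Background lipid therapy is already recorded on the CRF (Protocol 7.3, SAP 4.3), so the change needs a sentence and a subset flag and no new data. The price is a smaller n. The restriction corrects the level of the mean, but comparisons between arms among users will remain imprecise and should not be presented as evidence for or against an interaction. Showing total PCSK9 by background PCSK9-inhibitor status is optional; in 57 patients it would give small cells.
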